8.2.5 ADVERSE EVENT REPORTING

Deaths and unexpected, but definite, probable, or possibly-related SAEs are reported to the PI and DSMB within 48 hours through the use of an e-mail transmitted SAE report form copied to the PI, executive secretary of the DSMB, and DSMB Chair.

In addition, all events that meet the definition of an unanticipated problem (in the PI's opinion) should be reported to the UW IRB within 10 days using the Zipline Online portal.

An unanticipated problem is a problem or event that meets **all** of the following criteria:

- Unexpected – The harm (or potential harm) is inconsistent with risk information previously reviewed and approved by the Institutional Review Board (IRB) in terms of nature, severity, or frequency as well as the characteristics of the study population.
- Related or probably related to participation in the research;
 - Probably related: There is a reasonable probability (more likely than not) that the incident, experience or outcome may have been caused by the procedures involved in the research, or that it is associated with the use of any drug, biologic, or medical device that is part of the research.
- Suggests that the research places (or did place) one or more subjects or others at a greater risk of harm than was previously known or recognized. This includes physical, psychological, economic, educational advancement, or social harm.

Reports are required within 24 hours for qualifying medical problems covered by the UW Human Subjects Assistance Program (HSAP), a breach of confidentiality, or inappropriate use of protected health information.

In addition, the IRB requires a report within 10 days for serious non-compliance, continuing non-compliance (serious or non-serious), emergency deviation from IRB approved procedures to eliminate an apparent hazard to subjects or others, complaints that cannot be resolved by the research team, audit notification from a federal agency, information that indicates a new potential risk (e.g. new publication), and all DSMB reports.

Expected S(AE)s are not required to be reported to the UW IRB outside of continuing review.

8.2.6 REPORTING EVENTS TO PARTICIPANTS

Participants will be updated with any learned information during the study that may affect their willingness to participate.

8.2.7 EVENTS OF SPECIAL INTEREST

Not applicable.

8.2.8 REPORTING OF PREGNANCY

Pregnancy and the post-partum period is a highly dangerous and volatile time for women with pulmonary arterial hypertension and as a result participants who are pregnant, lactating, or have

evidence of dynamic disease with pulmonary vasodilator adjustment within 30 days of randomization will not be included. It is also possible that harmful side effects that are not yet known could happen to both the mother and unborn or breast-feeding child.

The investigator must be notified immediately if the subject becomes pregnant and they will be withdrawn from the study. This is anticipated to occur uncommonly if ever. The clear clinical recommendation in pulmonary arterial hypertension is dual-method contraception and the risk of death with pregnancy is prohibitive. Unintended or intended pregnancy is a very rare event in the pulmonary vascular disease clinic.

9 STATISTICAL CONSIDERATIONS

9.1 STATISTICAL HYPOTHESES

Primary Efficacy Endpoint(s): The primary endpoint is the difference in 6-minute walk distance.

Secondary Efficacy Endpoint(s): The secondary endpoint is the difference between treatment groups in BNP, NYHA functional class, TAPSE, right ventricular basal diameter, emPHasis-10 score, and number of participants with an escalation of routine clinical treatments for PAH for each visit.

We hypothesize that famotidine use in individuals with PAH will improve 6-minute walk distance over 24 weeks relative to placebo.

We further hypothesize that over 24 weeks famotidine use in individuals with PAH will lower BNP, improve the NYHA functional class, increase the TAPSE, diminish the right ventricular basal diameter, improve the emPHasis-10 score, and minimize the need to escalate routine treatment for PAH (diuretics and pulmonary vasodilators).

9.2 SAMPLE SIZE DETERMINATION

The primary endpoint is the change in six-minute walk distance. The study was powered to detect a difference of 31.9 meters. A 31.9 meter improvement in 6MWD is well aligned with established thresholds for a minimally important difference in patient reported outcomes. The 6MWD was chosen because 6MWD is a surrogate for patient-centered outcomes and was the primary endpoint in labeling trials for most of the medications used to treat pulmonary arterial hypertension (PAH).

The field is appropriately shifting toward larger event driven trials; however, we did not feel a larger event driven trial of famotidine was warranted at this juncture. The current proposal is the first randomized evaluation of this drug and this pathway in individuals with right heart failure and/or PAH and a smaller Phase II trial was felt to be a more appropriate next step.

For the RHC sub-study, the initial sample size was set at 10 participants based on the following power to detect large differences.

Size of difference	SV index (mL/m ²)	Total sample size	n per group	power
Large	20	10	5	0.87
Medium-high	15	10	5	0.67
Medium-low	10	10	5	0.36
Small	5	10	5	0.13

As the study progressed, recruitment into this invasive arm appeared to be more feasible and the sample size was increased to 20 participants.

Size of difference	SV index (mL/m ²)	Total sample size	n per group	power
Large	20	20	10	0.99
Medium-high	15	20	10	0.95
Medium-low	10	20	10	0.68
Small	5	20	10	0.23

9.3 POPULATIONS FOR ANALYSES

Intent-to-Treat Population: All subjects who are randomized will comprise the intent-to-treat (ITT) population. The ITT population will be analyzed for the primary and secondary endpoint analyses and will comprise the safety population used for all safety analyses.

Per Protocol Population: Subjects in the ITT population whose famotidine medication reconciliation suggest adherence to study drug for 80% or more of administered doses will be evaluated as the per protocol population. The per-protocol population will be used in the sensitivity analyses of the primary and secondary endpoints. A second per protocol population will include participants for whom H₂ receptor antagonists are detected by Mass Spectrometry at the final visit relative to those for whom H₂ receptor antagonists are not detected.

9.4 STATISTICAL ANALYSES

9.4.1 GENERAL APPROACH

Except where otherwise noted, all tests will be two-sided and statistical significance will be determined at the 0.05 level.

9.4.2 ANALYSIS OF THE PRIMARY EFFICACY ENDPOINT(S)

The primary endpoint is the difference between treatment groups in the change of 6-minute walk distance (6MWD) between baseline and 24 weeks. Linear regression will be performed with the change in 6MWD between baseline and 24 weeks as outcome and treatment group as the primary predictor of interest, adjusted for baseline 6MWD and baseline NYHA functional class as the stratification variable. The estimate of the treatment effect will be provided with associated 95% confidence interval (CI).

Missing 6MWD at 24 weeks will be imputed as follows. Subjects known to be dead before the 24 week assessment will have zero imputed for their 24 week 6MWD. Missing 24 week 6MWD for subjects who are alive will be imputed using multiple imputation. The imputation model will have prognostic variables as the predictor variables. Prognostic variables will include age, gender, and etiology of pulmonary hypertension, baseline six minute walk test, baseline right ventricular diameter, and baseline BNP. The multiple imputation will use Markov Chain Monte Carlo (MCMC), which assumes that the variables in the imputation model have a joint multivariate normal distribution (MVN). The number of imputations to be performed will be 100. One hundred is selected because it is not too large that it requires heavy computations and is not too small (such that the Monte Carlo error is still small enough at around 0.1 times the standard deviation). The “proc mi” procedure in SAS will be used to impute the missing observations.

Although every effort will be made to avoid missing data, a range of approaches to missing 6MWD will be considered as sensitivity analyses representing a range of conservative and anti-conservative biases to describe the range of possible differences.

Sensitivity Analyses of the Primary Endpoint

Sensitivity analyses of the primary endpoint will include:

- a linear regression model using a worst case scenario (WCS) method of imputation
 - a linear regression model of the 24 week 6MWD without imputation (complete case analysis)
- (1) The worst case scenario method of imputation will impute zero for all missing 6MWD at week 24.
(2) The linear regression method will model the 24 week 6MWD on treatment assignment, adjusting for baseline 6MWD and baseline NYHA class using least squares and robust standard error estimates. For all methods, treatment effect estimates and 95% CIs will be presented.

Additional Analyses of the Primary Endpoint

Additional analyses of the relative change in 6MWD will include the proportion of participants who achieve a minimally important change in 6MWD of 31.9 meters or greater. To test the null hypothesis that there is no difference between the treatment groups, logistic regression adjusted for the NYHA functional class (stratification variable) will be used. The difference between treatment groups will be provided with associated 95% CI. Subjects missing the 24 week 6MWD will not be counted as having achieved a minimally important change.

9.4.3 ANALYSIS OF THE SECONDARY ENDPOINT(S)

Summary statistics (mean, standard deviation, median and range) of BNP (untransformed and log-transformed), NYHA functional class, right heart strain, TAPSE, right ventricular basal diameter, emPHasis-10 score, and number of participants with an escalation of routine clinical treatments for PAH for each visit will be presented by treatment group. Change in these parameters (log-transformed value for BNP) will be evaluated between the treatment groups using linear regression adjusted for the value at baseline and NYHA functional class (stratification variable). The difference with 95% CIs will be reported.

The BNP is expected to vary by NYHA functional class. An additional sensitivity analysis will be performed with the difference of log-transformed BNP between baseline and week 24 as the outcome, with the predictor variables being baseline log-transformed BNP, treatment group, baseline NYHA functional class, and an interaction term between treatment group and baseline NYHA functional class.

Missing data in the secondary outcomes will be imputed in an analogous fashion to the primary outcome including sensitivity analyses to define the range of uncertainty imposed by missing data (worst case scenario and complete case analysis). The worst case scenario is different by variable. BNP and right ventricular basal diameter will be set to the highest value in the observed population. TAPSE will be assumed to be zero, emPHasis-10 score will be assumed to be 50, NYHA functional class will be assumed to be IV, and a participant will be assumed to have escalated PAH specific care.

9.4.4 SAFETY ANALYSES

All reported (S)AEs will be coded using MedDRA and grouped by body system. (S)AEs will be tabulated by treatment group using standard coding terms. Incidence of AEs by treatment arm will be tabulated by seriousness, severity, and relationship to study drug. If an AE is reported more than once for a given subject, the greatest severity and the worst-case relationship will be presented in tables. The number of SAEs and AEs will be summarized for each treatment group as follows: (i) The proportion of subjects with at least one (S)AE, (ii) The average number of (S)AEs per subject, and (iii) The rate of (S)AEs per

subject week of follow-up. Histograms showing the frequency of the number of (S)AEs in each treatment group will be included. Rates of (S)AEs by System Organ Class (SOC) will be presented by treatment group. Poisson regression modeling will be used to derive rate ratios and 95% CIs for each SOC. Rate ratios will be compared using a two-sided 0.05 level test for Poisson count data.

Safety lab data at each study visit and changes from baseline will be summarized by treatment group. In addition, clinical laboratory summaries will be presented by treatment group including: (i) incidence of significant abnormalities by visit; (ii) tables summarizing the frequencies of subjects below, within, and above the normal reference ranges at baseline and end of study; and (iii) tables displaying baseline to end of study shifts in each laboratory value (shifts between below, within or above normal range).

Although drug discontinuation is anticipated to be infrequent, the proportion of subjects permanently discontinuing study drug will be tabulated by treatment group. Drug discontinuation events will be categorized as: (1) Permanently discontinued study drug and (2) Permanently discontinued study drug and withdrew from study. The reason for permanent drug discontinuation will be summarized. The number of hospitalization events and proportion of subjects hospitalized from baseline to study termination will be summarized and compared by treatment group. Poisson regression modeling will be used to derive rate ratios and 95% CIs to compare hospitalization rates between treatment groups.

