8.2.2 DEFINITION OF SERIOUS ADVERSE EVENTS (SAE)

Any AE that results in any of the following outcomes:

- Death
- Life-threatening
- Event requiring inpatient hospitalization or prolongation of existing hospitalization
- Persistent or significant disability/incapacity

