6.6.1 Adverse Events

Adverse events (AEs) will be coded using the Medical Dictionary for Regulatory Activities (MedDRA), see Section 5.1, and displayed in tables and listings using System/Organ/Class (SOC) and Preferred Term (PT).

Analyses of adverse events will be performed for those events that are considered treatment emergent, where treatment emergent is defined as any adverse event with onset after the administration of study medication through the end of the study (see Section 5.2) or any event that was present at baseline but worsened in intensity or was subsequently considered drug-related by the investigator through the end of the study.

Adverse events are summarized by subject, therefore, in any tabulation, a subject contributes only once to the count for a given adverse event (SOC or preferred term).

The number and percentage of subjects with any treatment-emergent adverse event (TEAE), any treatment-emergent adverse event by severity, with any treatment-emergent adverse event by relationship to study drug, with any treatment-emergent adverse event leading to withdrawal from study drug, and with any treatment-emergent serious adverse event (SAE) will be summarized by treatment group and overall. In these tabulations, each subject will contribute only once (i.e., the most related occurrence or the most intense occurrence), regardless of the number of episodes. The number of events and the average number of events will also be provided in tabulations of TEAEs and serious TEAEs.

Adverse events with definite, probable, and possible relationship are considered related to study drug. Adverse events with unrelated and unlikely relationship are considered unrelated to study drug.

Histograms showing the frequency of the number of treatment-emergent AEs and SAEs in each treatment group will be included.

Exposure-adjusted event rates by treatment group and overall will be provided for participants with TEAEs, and with serious TEAEs. Each summary will present by decreasing incidence of PT per 100 subject years of exposure, calculated as (number of subjects with event/total patient-years). Years of exposure is either a) time from first treatment until start date of TEAE type or b) duration of exposure for subjects without a TEAE type. Poisson regression modeling will be used to derive rate ratios and 95% CIs for each SOC. Rate ratios will be compared using a two-sided 0.05 level test for Poisson count data.

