The number and percentage of subjects with TEAE with hospitalization required will be summarized by treatment group and overall, including the number of events, the average number of events and the exposure-adjusted event rates. Poisson regression modeling will be used to derive rate ratios and 95% CIs to compare hospitalization rates between treatment groups.

All adverse events occurring on study will be listed in subject data listings.

By-subject listings also will be provided for the following: subject deaths; serious adverse events; adverse events leading to withdrawal and adverse events with hospitalization required.

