7 CHANGES TO PLANNED ANALYSES

The following are changes between the protocol-defined statistical analyses and those presented in this statistical analysis plan:

The FAS will be the primary analysis set for the analysis of the primary and secondary efficacy endpoints rather than ITT. FAS includes all randomized subjects who received at least 1 dose of study medication. Subjects will be analyzed according to their randomized treatment.

Safety analysis set will be the primary set for the analysis of the safety parameters and it includes all randomized subjects who received at least 1 dose of study medication. Subjects will be analyzed according to their actual treatment. Actual treatment is defined as the treatment received for most of the days during the treatment phase of the study.

The data of NYHA functional class will be considered to be ordinal categorical values in the analysis. Change from baseline in NYHA functional class will be evaluated between the treatment groups using logistic regression adjusted for the baseline NYHA functional class (stratification variable). Missing data will be imputed in an analogous fashion to the primary outcome including sensitivity analyses to define the range of uncertainty imposed by missing data (worst case scenario and complete case analysis) but for categorical variables.

The data of escalation of routine clinical treatments for PAH will be analyzed as a binary categorical variable (yes / no escalation). A Cochran-Mantel-Haenszel (CMH) test with adjustment for the stratification factor baseline NYHA functional class will be used to test the null hypothesis of no treatment effect during the trial for famotidine vs. placebo with regards to the proportion of subjects with an escalation of routine clinical treatments for PAH. Missing data will be imputed in an analogous fashion to the primary outcome including sensitivity analyses to define the range of uncertainty imposed by missing data (worst case scenario and complete case analysis) but for categorical variables.

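### The SAP replaces the protocol's hospitalization events with TEAEs flagged for hospitalization, without declaring it, and leaves the Poisson count undefined, so its hospitalization rate is not a rate of admissions.

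*Protocol*

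**What the plan says.** Protocol 9.4.4 treats hospitalization as an item of its own, apart from the adverse-event counts and rates in the same section: "The number of hospitalization events and proportion of subjects hospitalized from baseline to study termination will be summarized and compared by treatment group". It adds a Poisson rate ratio with a 95% CI for hospitalization rates. It does not define a hospitalization event.

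SAP 6.6.1 puts this in its place: "The number and percentage of subjects with TEAE with hospitalization required will be summarized by treatment group and overall". The same sentence asks for the total and mean count of such events and for their rates adjusted for exposure. The SAP then keeps the protocol's modelling sentence: "Poisson regression modeling will be used to derive rate ratios and 95% CIs to compare hospitalization rates between treatment groups". The count and the person-time for that model are not stated.

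Earlier in SAP 6.6.1 the exposure-adjusted rate is "calculated as (number of subjects with event/total patient-years", and a subject's exposure ends at the first event of the type in question. The same section starts the treatment-emergent window after study drug is first taken.

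Protocol 8.2.2 gives as one criterion for a serious adverse event: "Event requiring inpatient hospitalization or prolongation of existing hospitalization".

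SAP Section 7 opens with "The following are changes between the protocol-defined statistical analyses and those presented in this statistical analysis plan" and lists four: the full analysis set, the safety set, the handling of NYHA class, and the handling of PAH treatment escalation. Hospitalization is not among them.

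**The concern.** The protocol's unit is the hospitalization event. The SAP's unit is an adverse event carrying a hospitalization flag. The two agree only if every admission produces exactly one flagged TEAE, and nothing in the SAP ensures that. Two diagnoses behind one admission are two adverse events. A complication that prolongs the stay may be a third, if the flag covers prolongation.

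At stake is a pre-specified between-arm comparison with a rate ratio and interval. As the SAP stands, two competent programmers could model different counts from the same data and report different ratios, each consistent with the text. A reader would take either for a comparison of admission rates. Because Section 7 is silent, the reader would also not learn that the protocol's measure had been replaced.

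**Working it through.** **Step 1. The two documents side by side.**

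| Item | Protocol 9.4.4 | SAP 6.6.1 |
|---|---|---|
| Unit | Hospitalization event | TEAE flagged for hospitalization |
| Window start | Baseline | After first dose |
| Proportion hospitalized | Summarized and compared | Summarized only |
| Rate | Hospitalization rate, Poisson | Subjects with an event over patient-years, time cut at first event; plus a Poisson model with no stated count or offset |
| Link from TEAEs to one stay | Not applicable | None |

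The SAP's once-per-subject rule works per system organ class or preferred term in by-subject tables. It does not govern the number or average number of events. The window difference is short: both schedules put baseline at Day -14 to Day -1, so it is at most 14 days.

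**Step 2. How far the readings differ.** Neither document gives a hospitalization rate, so there is no planned figure to reproduce. From the documents: 80 subjects allocated 1:1 (40 per arm) and 24 weeks of treatment. With no dropout,

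person-time per arm = 40 × 168 / 365.25 = 18.4 patient-years.

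Assume for illustration that one arm has 6 admissions in 5 subjects, with 2 flagged TEAEs each. Per 100 patient-years:

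- Admissions: 100 × 6 / 18.4 = 32.6
- Flagged TEAEs: 100 × 12 / 18.4 = 65.2
- Subjects with an event: 100 × 5 / 18.4 = 27.2, slightly higher once time is cut at first event

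The two SAP readings fall on opposite sides of the admission rate.

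**Step 3. The test, if TEAE terms are the Poisson count.** Let K be the number of flagged terms per admission. If admissions are Poisson, the term count has variance/mean = E[K²]/E[K], where a Poisson model assumes 1. The overcount is E[K] − 1.

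| Assumed share with 1 / 2 / 3 terms | E[K] | E[K²] | Overcount | Variance/mean |
|---|---|---|---|---|
| 90 / 10 / 0% | 1.1 | 1.3 | 10% | 1.18 |
| 70 / 20 / 10% | 1.4 | 2.4 | 40% | 1.71 |
| 50 / 30 / 20% | 1.7 | 3.5 | 70% | 2.06 |

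Simulation: 200,000 trials, mean 10 admissions per arm, no true difference, Wald test on the log ratio of counts, two-sided 0.05.

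- Counting admissions: 4.1% rejection
- Counting terms: about 6%, 12% and 16% for the three rows

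With 6 or 15 admissions per arm, counting terms gives 4.5% to 16.5% across the same rows. The low end, at 6 admissions and 1.1 terms, shows no excess over 5%.

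**Step 4. The test, if subjects with an event are the count.** Each subject contributes at most once, so several terms from one stay cannot inflate the numerator. The excess in Step 3 does not arise, but second and later admissions are discarded.

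**The case against.** The strongest reply is that the SAP never says TEAE terms enter the Poisson model. Its only defined rate counts subjects, on which multiple coding has no effect. The number and percentage of subjects with a flagged TEAE is equally immune, and by-subject listings of these events are planned. The protocol does not define a hospitalization event, its schedule shows no separate record of admissions, and hospitalization otherwise appears only in the adverse-event definitions. The SAP may therefore simply be putting into practice the one data source the protocol describes. The SAP phrase also omits prolongation, so that route to an extra event depends on how the flag is recorded.

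Most of this stands, and it rules out several stronger readings that a reader might infer:

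- That the hospitalization rate ratio will be inflated or its interval too narrow. This follows only if terms are the count, which is not stated.
- That admissions without an adverse event are lost. The SAP wording would exclude them, but the protocol is not shown to have captured them, and its broad adverse-event definition may leave few.
- That admissions for therapy changes, hypothesized to be fewer on famotidine, go missing. The protocol hypothesizes less treatment escalation and says nothing about admissions. Escalation is analysed separately as a secondary endpoint.

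The reply does not remove the central point. Counting subjects once is not a rate of admissions either, the choice between the readings is left open, and Section 7 is silent.

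**Conclusion.** The point holds as an undeclared change of unit with an undefined count. Three things rest on the text alone: the protocol's hospitalization events became flagged TEAEs, no rule collapses TEAEs to one stay, and Section 7 omits the change. It also follows from the text that the event totals can count an admission more than once and that the exposure-adjusted rate drops readmissions.

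The size is conditional. Rejection of about 6% to 16% at a nominal 5% applies only if terms are the Poisson count, and rests on assumed figures (10 admissions per arm, 1.1 to 1.7 terms per admission). Under the subject-based definition there is no such inflation. Two smaller departures come with it: the later start of the window and the loss of the comparison of the proportion hospitalized.

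This is a safety analysis. It does not touch the primary endpoint, and no stopping rule depends on it. It is worth correcting because the repair is cheap and the comparison is pre-specified.

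**What to change.** In SAP 6.6.1:

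1. Define a hospitalization event as one inpatient admission, identified by admission date. Collapse flagged TEAEs from the same or overlapping stay into it, including any that only prolong the stay.
2. Use the number of admissions per subject as the Poisson outcome, with log follow-up time as offset. Use a robust or overdispersion-adjusted variance, since one subject may be admitted more than once.
3. State the counting window, from baseline as in the protocol.
4. Restore the between-arm comparison of the proportion hospitalized.
5. Keep the table of flagged TEAEs as descriptive.

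In SAP Section 7, list any departure from Protocol 9.4.4 that remains, such as a first-dose start or a restriction to adverse-event-related admissions.

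The cost is SAP wording, some programming, and admission dates from the serious adverse event records of the single site. The event count will be somewhat lower than a count of TEAE terms.
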